## **1.0 INTRODUCTION**

### **Study Design**

Non-randomized Phase II de-escalation clinical trial to establish recurrence rates, site of recurrence, survival and quality of life outcomes for early T-stage HPV positive oropharyngeal SCCA treated with upfront surgery and reduced dose radiotherapy. Eligible, consented and registered patients will undergo transoral robotic surgery and selective neck dissection. After pathologic evaluation, patients with early stage disease as defined below will be placed into surveillance protocol as outlined or assigned to adjuvant therapy, depending on risk factors. Patients with intermediate risk factors will receive postoperative radiotherapy alone (5000 cGy). Patients with poor prognostic features will receive concurrent chemoradiotherapy (5600 cGy) with weekly cisplatin. Patients taken off study (based on Section 9.2 “Criteria from Removal of Study”) will be followed for survival until the study ends. Any adverse events occurring thereafter in these patients will not be considered related to the study and will not be tracked or reported.

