## **6.0 STUDY PARTICIPATION**

### **6.1 Duration of Follow Up**

Participants will be followed for 5 years after completion of study treatment or until death, whichever occurs first through standard of care treatment after therapy as prescribed by the Investigator which can include clinic visits or other follow-up by other means. Participants removed from study for unacceptable adverse events will also be followed until resolution or stabilization of the adverse event.

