### **6.2 Criteria for Removal from Study**

Participants will be removed from study when any of the criteria listed below applies. The reason for study removal and the date the participant was removed must be documented in the study-specific case report form (CRF). Alternative care options will be discussed with the participant.

In the event of unusual or life-threatening complications, participating investigators must immediately notify the Principal Investigator, [name] at [contact]

- Patient is removed early from protocol therapy at PI's discretion
- Patient is found ineligible
- Patient completion of protocol requirements
- Unacceptable toxicity
- Pregnancy
- Adverse Event
- Progressive disease/ relapse
- Lost to follow-up (documented 3 attempts via telephone or signature confirmation letter)

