### **13.4 Reporting to the Study Center**

#### **13.4.1 Serious Adverse Event Reporting**

All serious adverse events that occur after the initial dose of study treatment, during treatment, or within 30 days of the last dose of treatment must be reported to the MSSM Overall Principal Investigator on the local institutional SAE form for the local IRB and electronically on the eRAP CRF. This includes events meeting the criteria outlined in Section 11.1.2, as well as the following:

- Grade 2 (moderate) and Grade 3 (severe) events that are unexpected and at least possibly related/associated with the intervention.
- All Grade 4 (life-threatening or disabling) events that are unexpected or not specifically listed in the protocol as not requiring reporting.

CONFIDENTIAL

This document is confidential. Do not disclose or use except as authorized.

- All Grade 5 (fatal) events while the participant is enrolled and actively participating in the trial OR when the event occurs within 30 days of the last study intervention.

Note: If the participant is in long term follow up, report the death at the time of continuing review.

Participating investigators must report each serious adverse event to the MSSM Overall Principal Investigator within 24 hours of learning of the occurrence by Fax and email. In the event that the participating investigator does not become aware of the serious adverse event immediately (e.g., participant sought treatment elsewhere), the participating investigator is to report the event within 24 hours after learning of it and document the time of his or her first awareness of the adverse event. Report serious adverse events by telephone, email or facsimile to:

[name] at Ph- [contact]    [[contact]](mailto:[contact])

Within the following 24-48 hours, the participating investigator must provide follow-up information on the serious adverse event. Follow-up information should describe whether the event has resolved or continues, if and how the event was treated, and whether the participant will continue or discontinue study participation.

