#### **13.7 Monitoring of Adverse Events and Period of Observation**

All adverse events, both serious and non-serious, and deaths that are encountered from initiation of study intervention, throughout the study, and within 30 days of the last study intervention should be followed to their resolution, or until the participating investigator assesses them as stable, or the participating investigator determines the event to be irreversible, or the participant is lost to follow-up. The presence and resolution of AEs and SAEs (with dates) should be documented on the appropriate case report form and recorded in the participant's medical record to facilitate source data verification.

CONFIDENTIAL

This document is confidential. Do not disclose or use except as authorized.

For some SAEs, the study sponsor or designee may follow-up by telephone, fax, and/or monitoring visit to obtain additional case details deemed necessary to appropriately evaluate the SAE report (e.g., hospital discharge summary, consultant report, or autopsy report).

Participants should be instructed to report any serious post-study event(s) that might reasonably be related to participation in this study. Participating investigators should notify the MSSM Overall Principal Investigator and their respective IRB of any unanticipated death or adverse event occurring after a participant has discontinued or terminated study participation that may reasonably be related to the study.

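### Section 1.0 rules adverse events after removal from study unrelated and unreported, which contradicts Sections 6.1, 13.1.4, 13.4.1 and 13.7

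*Combined protocol and SAP*

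**What the plan says.** Section 1.0 (Study Design) deals with patients taken off study under the removal criteria. They "will be followed for survival until the study ends", and then: "Any adverse events occurring thereafter in these patients will not be considered related to the study and will not be tracked or reported". The paragraph places the removal criteria in Section 9.2. In this protocol 9.2 is Specific Study Plans for the correlative work, and the removal criteria are in 6.2.

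Section 6.2 lists, among other reasons for removal, "Unacceptable toxicity", a separate entry for adverse event, and "Progressive disease/ relapse".

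Other sections set rules for the same patients or the same events:

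- 6.1: "Participants removed from study for unacceptable adverse events will also be followed until resolution or stabilization of the adverse event".
- 13.4.1: serious events after the first dose, during treatment, or "within 30 days of the last dose of treatment must be reported to the MSSM Overall Principal Investigator". Removed patients are not excepted.
- 13.7: all events up to 30 days after the last study intervention are followed to an endpoint. Investigators also notify the overall principal investigator and their IRB when there is "any unanticipated death or adverse event occurring after a participant has discontinued or terminated study participation that may reasonably be related to the study".
- 13.1.4: attribution has five levels, from definite to unrelated.
- 14.2: safety data are gathered for the whole of the study.

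Section 16.5 makes toxicity a secondary endpoint, reported as a rate per arm with an exact binomial 90% interval. Section 11.1.1 makes everyone who goes on to surgery evaluable for toxicity.

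**The concern.** The sentence in 1.0 does two things that the safety sections do not allow. It settles causality before any event has occurred, and it switches off recording and reporting once a patient is off study. Because toxicity and adverse events are themselves grounds for removal, the rule reaches patients who tolerated treatment poorly. Because relapse is also a ground, it reaches Group I patients during the salvage therapy laid out in 5.2, whose outcomes are the subject of primary objectives 1.1.7 and 1.1.8.

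Two things are at stake. Sites have conflicting instructions on whether a serious event must be reported, in a trial where a participating site also delivers radiotherapy and chemotherapy (Appendix 4). And if some sites follow 1.0, removed patients stay in the denominator of the toxicity rate while new events in them never reach the numerator. Less long-term toxicity is the case for de-escalation made in Sections 2.2 and 2.3, so under-counting would favour the trial's own argument.

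**Working it through.** The plan gives no figure on this point, so the check is a comparison of the rules, followed by the logic of the endpoint.

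**1. The rules side by side, for a patient off study**

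| Question | Section 1.0 | Elsewhere |
|---|---|---|
| Is the event that caused removal followed further? | No tracking | Yes, until it clears or stabilises (6.1) |
| Is a serious event within 30 days of the last dose reported? | No | Yes (13.4.1) |
| Is any event within 30 days of the last intervention followed? | No | Yes (13.7) |
| Is a later, unanticipated, possibly related event notified? | No | Yes (13.7) |
| How is relatedness decided? | Declared absent in advance | Five-level attribution (13.1.4) |

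**2. A test case.** A patient in Group IIIA or IIIB is removed for toxicity in week 4 of chemoradiotherapy and has a new serious event 10 days after the last dose. Ten days is inside the 30-day window, so 13.4.1 requires a report and 13.7 requires follow-up. Section 1.0 says the event is unrelated and is not reported. No conduct satisfies both. Section 6.1 does not decide this case, because it covers the event that led to removal and not a new one.

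**3. What following 1.0 would lose, and what it would not**

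- Kept: the toxicity that triggers removal, which precedes removal; and deaths, through survival follow-up.
- Lost: the later course of that toxicity, new non-fatal events, and their attribution.

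**4. Effect on the toxicity rate.** Let n be the evaluable patients in a group, a the number with a qualifying toxicity recorded before removal (or at any time if never removed), and b the number whose first qualifying toxicity comes after removal.

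- Rate if 1.0 is followed: a/n
- Rate if all such events are counted: (a + b)/n
- Difference: b/n, which is zero or positive

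So the error can only lower the reported rate. A patient removed for a toxicity that itself qualifies is already in a, and later events in that patient do not change an any-toxicity rate. The loss falls on patients removed for other reasons, such as relapse, and on any separate rate for late or new toxicity. The documents give neither a nor b, nor an expected removal rate, so b/n cannot be computed.

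**The case against.** There are three fair replies.

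*The sentence may mean something else.* The preceding sentence ends at the close of the study, so *thereafter* could mean after the study ends. The 30-day rules would then largely escape conflict. This reading is possible but strained: the subject is patients taken off study, who are left with survival follow-up only. Nor does it remove the conflict. Section 13.7 asks that participants be told to report serious post-study events that may be related, and blanket non-relatedness still clashes with 13.1.4.

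*Section 1.0 is only an introduction.* Sections 6, 13 and 14 govern conduct and already require most of this work. The Reporting of Serious Adverse Events text in Section 14 sends deaths and unexpected serious events to the IRB within 24 hours and to the DSMB chair within 72 hours. This stands in part: loss of data follows only where staff obey 1.0. A reader might infer that the plan withholds treatment-related events from the DSMB and IRB. The documents do not establish that; they establish conflicting instructions, and I see no statement of which section prevails.

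*The worst toxicity is not lost.* This also stands. A reader might infer that the most severe outcomes vanish from the analysis, but the triggering event and any death are retained. Nor is everyone who tolerates treatment poorly removed: Section 7.2 provides holds, reductions and substitution.

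**Conclusion.** The contradiction is real, lies in current text, and should be fixed. As written, Section 1.0 would give wrong reporting and wrong attribution for events in removed patients. The conclusion rests on reading *thereafter* as after removal; on the other reading a narrower conflict with 13.7 and 13.1.4 remains.

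The consequence is conditional. Where a site follows 1.0, the later course of toxicity and new non-fatal events are dropped, and the toxicity endpoint could be biased downward for late or new events. The direction is certain; the size is not derivable.

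It is tempting to take the 35% severe late toxicity rate that Section 2.2 cites for oropharyngeal cancer and shrink it by an assumed share of removed patients. The documents do not support that. The figure comes from earlier chemoradiotherapy trials, not from reduced-dose treatment after surgery. It includes treatment-related deaths, which survival follow-up would still catch. And the shrinkage would count patients removed for toxicity as event-free, when in a per-patient rate they are already events.

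**What to change.** Reconcile the sections as follows.

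1. Delete the final sentence of the Study Design paragraph in 1.0 and refer instead to 6.1, 13.4.1 and 13.7. Events in removed patients that fall under those rules are recorded, attributed under 13.1.4 and reported, whatever the reason for removal.
2. State in 16.5 that these events count in the group's toxicity rate.
3. Correct the cross-reference in 1.0 from Section 9.2 to Section 6.2.
4. State whether salvage therapy under 5.2 counts as a study intervention for the windows in 13.4.1 and 13.7, since neither section says.

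The cost is a short amendment. Most of the work is already required elsewhere in the protocol. Reported toxicity may be slightly higher. The change has a limit: beyond 30 days, 13.7 asks only for unanticipated events that may be related, so expected late effects in removed patients would still not be collected systematically.

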### **1.1 Primary Objectives**

- 1.1.1 To determine the rate of local regional control (LRC) at 5 years in patients with early and intermediate stage HPV related oropharynx cancer treated with surgery alone.
- 1.1.2 To determine the rate of progression free survival (PFS) at 5 years in patients with early and intermediate stage HPV related oropharynx cancer treated with surgery alone.
- 1.1.3 To determine overall survival (OS) at 5 years in patients with early and intermediate stage HPV related oropharynx cancer treated with surgery alone.
- 1.1.4 To determine the rate of local regional control (LRC) at 3 years in patients with HPV related oropharynx cancer treated with a de-intensified adjuvant protocol.
- 1.1.5 To determine the rate of progression free survival (PFS) at 3 years in patients with HPV related oropharynx cancer treated with a de-intensified adjuvant protocol.
- 1.1.6 To determine overall survival (OS) at 3 years in patients with HPV related oropharynx cancer treated with a de-intensified adjuvant protocol.
- 1.1.7 To determine the rate of PFS (Ultimate Disease Control – UDC) and of OAS after secondary therapy for patients treated with surgery only who have local regional relapse at 5 years
- 1.1.8 To determine the rate of PFS (UDC) and OAS after secondary therapy for patients who relapse with distant disease after surgery only
- 1.1.9 To quantify the quality of life of patients treated with this protocol at 3 years

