## 11.0 MEASUREMENT OF EFFECT

### 11.1.1 Definitions

Evaluable for toxicity. All participants who go on to surgery will be evaluable for toxicity from the time of their first treatment. Patients who are screened will be evaluated and the reason for screen failure will be recorded

Evaluable for Primary Outcome: Only patients who are entered and have surgery will be eligible for assessment of the primary outcomes (LRC, PFS). All patients who have had surgery will be analyzed on an ITT for LRC, PFS, and survival.

Progression-Free Survival: Progression-Free Survival (PFS) is defined as the duration of time from start of treatment to time of objective disease progression or death.

Local Regional Control (LRC) will be defined as local and regional control of disease, censored for death.

Overall Survival (OAS) will be defined as alive at the time of analysis, this will be analyzed as for the entire trial, for all randomized patients and only for those patients randomized who received one dose of radiotherapy.

Post Recurrence LRC: Surveillance Patients who recur will be assessed for LRC post treatment for their initial recurrence

Post Recurrence PFS Surveillance Patients who recur will be assessed for PFS post treatment for their initial recurrence

Ultimate Disease Control will be defined as those patients who are alive and disease free at the time of analysis

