In this study, patients will complete the EORTC QLQ-C30, EORTC QLQ H&N35, MDASI-HN, the MDADI-HN (dysphagia) and xerostomia questionnaires prior to therapy and then at 3, 6, 12 and every 12 months after therapy for 5 years for all patients. During the concomitant chemo-radiation phase of treatment, in order to avoid patient fatigue, the EORTC QLQ-C30, EORTC QLQ H&N35, MDASI-HN module, MDADI-HN (dysphagia) and xerostomia questionnaires will be completed on pre and weeks 5, 7 and post rx 3 months; and the . The adverse events assessments, the (see table). As shown in the statistical plan we will use these assessments in conjunction with adverse events assessments to compare the experiment and control arms of this study.

	Pre-Study	CRT	Post-Study Follow-up
Informed Consent	To be obtained before enrollment		
EORTC QLQ-C30, EORTC QLQ H&N35	Within 10 days before registration	pre and weeks 5 7 and post rx 3 months	3, 6, 12, and every 12 months for 5 years
MDASI-HN	Within 10 days before registration	pre and weeks 5 7 and post rx 3 months	3, 6, 12, and every 12 months for 5 years
MDADI-HN (Dysphagia Assessment Questionnaire)	Within 10 days before registration	pre and weeks 5 7 and post rx 3 months	3, 6, 12, and every 12 months for 5 years
Xerostomia		pre and weeks 5 7 and post rx 3 months	3, 6, 12, and every 12 months for 5 years

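### Removal from study at relapse conflicts with the 5-year questionnaire schedule, so 3-year quality of life may omit patients who relapsed and were salvaged

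*Combined protocol and SAP*

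**What the plan says.** **The objective.** Section 1.1 lists as a primary objective (1.1.9): "To quantify the quality of life of patients treated with this protocol at 3 years". It covers every treatment group. Section 16.1 places QOL among the secondary objectives, and Section 16.4 does not name it as a primary endpoint.

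**The collection schedule.** Section 12.0 has the instruments completed "prior to therapy and then at 3, 6, 12 and every 12 months after therapy for 5 years for all patients". It names no stop at relapse. Section 6.1 adds: "Participants will be followed for 5 years after completion of study treatment or until death, whichever occurs first".

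**The removal rule.** Section 6.2 states: "Participants will be removed from study when any of the criteria listed below applies". One listed criterion is "Progressive disease/ relapse". The Study Design paragraph in Section 1.0 says patients taken off study "will be followed for survival until the study ends", and that their later adverse events will be neither tracked nor reported. It points to a Section 9.2 for the removal criteria. Those criteria are in 6.2; Section 9.2 describes the correlative studies.

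**What is kept after relapse.** Objective 1.1.7 asks for disease control and survival "after secondary therapy for patients treated with surgery only who have local regional relapse at 5 years", and 1.1.8 asks the same after distant relapse. Section 11.1.1 says: "Surveillance Patients who recur will be assessed for PFS post treatment for their initial recurrence", and defines local regional control after recurrence in the same way. None of these mentions QOL.

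**The concern.** Two sets of instructions lead to different data. Under Section 12.0, a Group I patient who relapses at 18 months still completes the 36-month forms. Under 6.2 with the Study Design paragraph, that patient has left the study and is contacted for survival.

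The forms lost in this way would not be lost at random. Section 5.2 sends relapsed Group I patients to salvage surgery followed by chemoradiotherapy, definitive chemoradiotherapy, or TPF-based treatment, depending on the extent of recurrence. Section 2.2 itself links radiation dose to dysphagia, feeding-tube dependence and aspiration. The rationale for surgery alone is that most patients are spared that burden while a minority is salvaged. A 3-year QOL result that leaves out the salvaged minority omits the cost side of the strategy. Because adverse events after removal are also not tracked, that cost might have no other data source. Forms not collected at 36 months cannot be recovered later.

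**Working it through.** The documents give no QOL sample size, standard deviation, margin or expected score, so there is no planned QOL figure to reproduce. The check has two parts.

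**1. The sections side by side**

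| Question | Section | Reading |
|---|---|---|
| Does relapse remove a participant? | 6.2 | Yes |
| What is collected after removal? | 1.0, Study Design | Survival is named; later adverse events are excluded |
| Who completes questionnaires, and for how long? | 12.0 | All patients, to 5 years |
| How long is follow-up? | 6.1 | 5 years or death |
| Which outcomes are assessed after relapse? | 1.1.7, 1.1.8, 11.1.1 | Local regional control, progression-free survival or ultimate disease control, overall survival |
| How is QOL analysed, and how is relapse handled? | 16.1 to 16.5 | Not stated |

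The first two rows imply that questionnaires stop at relapse. The next two imply that they continue. The fifth shows that follow-up after relapse goes beyond survival, but it does not extend to QOL. The sixth shows that the analysis plan does not settle the matter.

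**2. Size if 6.2 governs (illustration for Group I)**

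Inputs:
- Group I size: 100 (Section 16.2).
- Recurrence grid: 10, 20, 30, 40 and 50% (Section 16.2). No time point is given.
- r: the share of patients alive at 3 years who have relapsed.
- D: the mean QOL deficit in relapsed patients on a 0-100 scale where higher is better. It is not in the documents; 10 and 20 points are assumed.

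If relapse-free patients have mean m, the mean over all living patients is (1 − r)m + r(m − D) = m − rD. The relapse-free mean therefore overstates the whole-group mean by r × D.

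If the grid holds at 3 years, r is taken directly from it. If it holds at 5 years with constant hazard (assumption), the 3-year share is 1 − (1 − r)^(3/5). For example, 1 − 0.5^0.6 = 0.340.

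| Grid value | Group I patients with 3-year forms, 3-year reading | Shift, D = 10 / 20 | 3-year share, 5-year reading | Shift, D = 10 / 20 |
|---|---|---|---|---|
| 10% | 90 | 1 / 2 | 6.1% | 0.6 / 1.2 |
| 20% | 80 | 2 / 4 | 12.5% | 1.3 / 2.5 |
| 30% | 70 | 3 / 6 | 19.3% | 1.9 / 3.9 |
| 40% | 60 | 4 / 8 | 26.4% | 2.6 / 5.3 |
| 50% | 50 | 5 / 10 | 34.0% | 3.4 / 6.8 |

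The counts ignore deaths and ordinary missing forms. A patient who relapses and dies before 36 months has no 3-year form under any rule, so deaths after relapse lower r and the shifts.

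**The case against.** A reader might infer that the protocol ends QOL collection at relapse. The documents do not say so. Section 12.0 is the only rule written for QOL, and it covers all patients to 5 years. The study calendar in Section 10.0 also schedules the dysphagia questionnaire to 36 months with no relapse stop. The Study Design paragraph does not say that survival is the only thing collected, and its wrong cross-reference makes it a weak authority. Objectives 1.1.7 and 1.1.8, Section 11.1.1 and the salvage plan in 5.2 show that survival-only follow-up cannot be meant literally for relapsed Group I patients. All of this stands, and it makes the point an unresolved contradiction rather than a stated stopping rule.

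A reader might also take 1.1.9 as an objective about surgery alone. It covers all groups, so the removal rule would affect Groups II and III too.

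The size is open to challenge as well. The recurrence grid illustrates credible bounds and is not a forecast. Its upper end is an edge case: Section 16.1 hypothesises local regional control above 50%, and the Section 14.2 boundaries stop the trial if recurrence above 50% becomes probable enough. No section supplies D. These objections limit the arithmetic to an illustration.

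They do not remove the conflict. The outcomes that the plan explicitly keeps after relapse leave QOL out, and a site that removes a relapsed patient and stops the forms is applying 6.2 as written.

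**Conclusion.** The point holds as a contradiction with a predictable direction of bias. Sections 6.2 and 1.0 can be read as ending QOL collection at relapse, Sections 12.0 and 6.1 say otherwise, and Section 16.0 does not resolve it. If sites follow 6.2, 3-year QOL would be observed only in relapse-free patients, would omit the burden of salvage, and would favour the strategy. This matters most in Group I, and it applies whether QOL is primary (Section 1.1) or secondary (Section 16.1).

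The possible overstatement of the Group I mean is about 1 to 10 points if the Section 16.2 grid is a 3-year rate, and about 0.6 to 7 points if it is a 5-year rate with constant hazard, less the effect of deaths after relapse. Both ranges rest on an assumed D of 10 to 20 points. The documents do not support the stronger conclusion that Group I QOL is bound to be measured only in patients who never had salvage, because a site following Section 12.0 would collect the forms.

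**What to change.** Reconcile Section 6.2, the Study Design paragraph (including its reference to Section 9.2) and Section 12.0:

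- State that relapse does not end questionnaire collection. Living patients in every group continue all instruments on the existing Section 12.0 schedule. Its after-therapy anchor stays tied to the initial protocol therapy and does not restart at salvage.
- In Section 16.0, define the 1.1.9 analysis in all living patients of each assigned group, regardless of relapse or salvage. Report the relapse-free subset as supportive.
- Report deaths and missing forms by relapse status.

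The cost is a wording amendment with no change to treatment. The instruments already exist and can be sent by mail or completed by phone alongside the survival contact already required. The downside is some questionnaire burden on relapsed patients and probably lower completion among them.
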